#### **IV. a. Number of Subjects**

It is expected that we will have 32 volunteers, 16 females and 16 males, complete full-length closed-loop experiments (5 days of closed-loop BG control). We will attempt to recruit participants in roughly equal numbers in the following age cohorts: 12-13 years, 14-16 years, and 17-20 years. We expect that the experiments can be accomplished over a period of 4-6 months. Up to 64 volunteers with type 1 diabetes will be enrolled, 32 females and 32 males. The upper bound is based on the expectation that some volunteers will be excluded after the screening visit and the possibility that some experiments may have to be discontinued before completion (due to, for instance, intercurrent illness or subject withdrawal). Studies will be conducted sequentially at the two proposed sites.

We will also ask non-participants meeting who are attending camp at the same time and who meet key criteria for study inclusion (age 12-20, use of insulin pump) for permission to review their camp records and to document pre-meal, pre-snack, bedtime, and midnight glucose values, as well as glucose interventions for hypoglycemia, and to get the result of their last A1c test prior to attending camp.

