The study physician or nurse practitioner will also answer any questions that the subject may have during their participation. They will share any new information in a timely manner that may be relevant to the subject's willingness to continue participating in the trial. The subjects may choose to discontinue their participation at any time. Subjects and subject guardians will be informed that obtaining screening labs does not necessitate or guarantee participation in the study.

Non-participants will receive a one page information sheet. They will have the opportunity to ask a study staff member any questions they may have. Verbal consent will be obtained. If they consent they will be asked to sign a release of medical information form requesting only the latest hemoglobin A1c result and provide the fax number and/or address of their physician.

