- Camp nurses will be asked to document all hypoglycemia and carbohydrate interventions for hypoglycemia.
- Camp nurses and counselors will be asked to maintain a schedule of active and less active sessions for each camper.
- As a difference from the camp usual care protocol, BG levels will be measured at midnight and 3:45 AM (regardless of the value at 12:00 AM) using the HemoCue point of care BG meter. There may be additional BG checks between 11 pm and 7 am as determined by a nocturnal hypoglycemia alert system (see closed-loop section below). Extra BG checks may be performed during the day depending on how many episodes of hypoglycemia occur (which trigger more frequent measurements), or on order of the resident camp physician.
- The only other difference from usual camp protocol is that hypoglycemia intervention rules will follow the same protocol as in the closed-loop BG control group (described below).
- At 3:00 PM on day 6 (Friday) the usual care portion of the experiment will end. The DexCom CGM will be removed.
- The volunteer's insulin pump will be downloaded for information on insulin dosing and carbohydrate intake during the usual care period.

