**Secondary endpoint analyses - BG:**

- All of following metrics will be generated from the HemoCue data during the closed-loop period and the usual care period, and the difference between the two periods will be reported unless otherwise specified:
- Average BG as determined from all HemoCue measurements taken during the day/nighttime including all extra measurements taken before meals, taken during exercise, and taken for hypoglycemia monitoring.

- Percentage of the above subset of BG values less than 70 mg/dl.
- Average BG as determined from the pre-meal, before bed, 12:00 AM, and 3:45 AM HemoCue measurements (6measurements per day)
- Percentage of the above subset of BG values less than 70 mg/dl.
- Percentage of subjects with mean BG < 154 mg/dl using all BG values
- Difference in the percentage of subjects with mean BG < 154 mg/dl using before meal and before bedtime BG values only
- Percentage of study days with mean BG < 154 mg/dl
- Number of hypoglycemic events as determined from all HemoCue measurements
- Nadir BG for each hypoglycemic event as determined from HemoCue measurements
- Fraction of scheduled BG measurements within each of the following glucose ranges as determined from all HemoCue measurements :
  - < 70 mg/dl
  - 70-120 mg/dl
  - 70-180 mg/dl
  - >180 mg/dl
  - >250 mg/dl
- Risk of hypoglycemia and hyperglycemia >180 mg/dl and >250 mg/dl during hours with vs. without bionic pancreas downtime
- Difference of outcome measures on day 1 vs. remaining days (days 2-5) and on day 1-2 vs. on remaining days (days 3-5)
- Difference in average BG as determined from the pre-meal, before bed, and 12:00 AM measurements between the non-participants and the open-loop and closed-loop arms.
- Percentage of the above subset of BG values less than 70 mg/dl between the non-participants and the open-loop and closed-loop arms.
- Difference in the percentage of subjects with mean BG < 154 mg/dl using before meal and before bedtime BG values only between the non-participants and the open-loop and closed-loop arms.
- Number of hypoglycemic events as determined from all BG measurements
- Nadir BG for each hypoglycemic event as determined from BG measurements
- Fraction of scheduled BG measurements within each of the following glucose ranges as determined from all BG measurements :
  - < 70 mg/dl
  - 70-120 mg/dl
  - 70-180 mg/dl
  - >180 mg/dl
  - >250 mg/dl

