- Total number of grams of carbohydrate taken for hypoglycemia during the daytime ((7:00 AM – 11:00 PM)
- Number of carbohydrate interventions for hypoglycemia overnight (11:00 PM – 7:00 AM)
- Total number of grams of carbohydrate taken for hypoglycemia overnight (11:00 AM – 7:00 AM)

We will calculate means, median, percentages, standard deviations, standard errors, inter-quartile

ranges, and 95% confidence intervals in descriptive analyses. We will use paired t-test for comparison of means. We will use multivariate regression models with repeated measurements to compare means and percentages while adjusting for patient demographics characteristics (age, gender).

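### Non-participant comparisons leave out the A1c already collected for both groups, and their event and nadir bullets rest on unequal night-time detection

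*Combined protocol and SAP*

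**What the plan says.** **Comparison and model.** Section VI. b. (secondary BG endpoints) compares average BG, the percentage of readings below 70 mg/dl and the percentage of subjects with mean BG below 154 mg/dl "between the non-participants and the open-loop and closed-loop arms". The closing paragraph of VI. b. names paired t-tests and a repeated-measures regression "adjusting for patient demographics characteristics (age, gender"). No other covariate is named anywhere.

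**A1c.** Section IV. a. says non-participants will be asked for permission to review their camp records "and to get the result of their last A1c test prior to attending camp". Section IV. c. adds a medical release "requesting only the latest hemoglobin A1c result". For volunteers, A1c is part of screening (V. a., V. d. i.) and of the pre-experiment data (VI. a.).

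**Readings used.** The mean BG and below-70 comparisons with non-participants are limited to pre-meal, bedtime and midnight values, and the below-154 comparison to pre-meal and bedtime values. The list then continues with "Number of hypoglycemic events as determined from all BG measurements", a matching nadir bullet, and a range-fraction bullet whose wording refers both to scheduled readings and to all readings.

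**Checking schedule.** For volunteers in usual care, "BG levels will be measured at midnight and 3:45 AM (regardless of the value at 12:00 AM") is the stated rule, and the closed-loop section repeats it. An alert system can prompt further checks between 11 PM and 7 AM in both arms. Under the camp routine (V. d. ii.), a 3:00 AM check follows only if the midnight check needed intervention. Other overnight checks are at the camp physician's discretion. The opening of section V rules out real-time monitoring of non-participants.

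**The concern.** Volunteers and non-participants differ by self-selection and by design. Volunteers pass the full exclusion list in III. b., which includes hypoglycemia unawareness, recent hypoglycemic seizure or coma, high insulin dose and insulin omission. Non-participants need only meet key criteria such as age and pump use. Prior glycemic control is therefore an obvious confounder. A1c is the one baseline measure of it obtained for both groups, yet no analysis is said to use it.

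The second problem is detection. A count of hypoglycemic events depends on how often, and when, someone looks. Volunteers are checked every night at 3:45 AM and also when an algorithm predicts a low. Non-participants are not. At the same true glucose, more events would be recorded in volunteers, so the bias works against both trial arms and could hide a real advantage. For nadirs the values are equally non-comparable, but the direction is not fixed.

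**Working it through.** The plan states no sample size or power for this comparison (VI. c. gives none at all), so the check covers the checking schedules and the A1c scale.

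**1. Scheduled checks**

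- Volunteers: 3 pre-meal + 1 bedtime + 1 midnight + 1 at 3:45 AM = 6 a day. This reproduces the six per day given in the secondary BG list.
- Non-participants: the same without 3:45 AM = 5 a day.
- Over five days: 6 × 5 = 30 against 5 × 5 = 25, ratio 30/25 = 1.20.
- At the closed-loop minimum of seven a day (V. c.): 35/25 = 1.40.

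**2. Alert-triggered checks**

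- Validation data in V. d. iii.: 29 extra checks in 48 nights, 29/48 = 0.60 per night.
- Checks with BG below 70 mg/dl: 10 + 14 = 24, and 24/48 = 0.50 per night. The extra checks are concentrated on lows.
- Adding 0.60 × 5 ≈ 3 checks over five days: 33/25 = 1.32, or 38/25 = 1.52 from the closed-loop minimum.

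**3. Effect on detected lows at identical glucose**

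Expected low readings over five days = scheduled checks × risk per check + 5 × alert-detected lows per night. The risk per check is an assumption; 5% is used here.

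| Scenario | Volunteers | Non-participants | Ratio |
|---|---|---|---|
| 3:45 AM check only | 30 × 0.05 = 1.5 | 25 × 0.05 = 1.25 | 1.2 |
| plus 0.1 alert lows per night (assumed) | 1.5 + 0.5 = 2.0 | 1.25 | 1.6 |
| plus 0.5 per night (validation rate) | 1.5 + 2.5 = 4.0 | 1.25 | 3.2 |

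With risks of 2% to 8% per check, the ratio runs from 1.2 (no alert lows) to 6.2 (2% risk at the validation rate). The upper end is a ceiling. It ignores non-participants' symptomatic and conditional night checks, the alert rate comes from an earlier closed-loop study, and readings are not the same as events. On shared times only, both groups have 25 scheduled readings and the ratio is 1.00.

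**4. A1c**

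- Slope from section I. b.: (212 − 154)/(9 − 7) = 29 mg/dl per point. Other pairs in the protocol (6.5% and 140, 7.4% and 164, 7.5% and 169), each set against 7% and 154, give 28, 25 and 30.
- Assumed imbalance of 0.3 to 0.5 points, full carry-over to camp BG: 0.3 × 29 = 8.7 and 0.5 × 29 = 14.5 mg/dl.
- Same imbalance, assumed 30% carry-over: 8.7 × 0.3 = 2.6 and 14.5 × 0.3 = 4.4 mg/dl.

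**The case against.** Several points on the other side stand.

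- *Matched times already exist.* A reader might infer that every non-participant comparison suffers from unequal sampling. The documents do not support that: the three bullets that name non-participants all use readings both groups share.
- *Range fractions.* A reader might also infer that these are inflated by extra checks. The bullet says both scheduled and all, so it is ambiguous. Extra readings raise a count, but they do not by themselves raise a fraction.
- *Scope is inferred.* The later event and nadir bullets do not name non-participants. Their position after the three that do, the change from HemoCue to BG in the wording, and the collection of events and nadirs for non-participants in VI. a. make the reading likely, not certain.
- *The scheduled gap may be small.* Section V. c. puts standard camp checking at six to seven a day, with occasionally one or two extra for volunteers. The routine 3:45 AM and alert checks are the asymmetry that remains.
- *Carry-over is unlikely to be full.* At camp, a physician rewrites insulin orders, basal rates are typically cut by about 20%, and targets and supervision are common to all campers.
- *The adjustment sentence is general.* It is not tied to this comparison. But no other model is given, and a paired t-test cannot be applied to unpaired non-participants.
- *Discarding readings has a price.* Using shared times alone would drop symptomatic lows, so the all-readings counts should stay alongside.

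**Conclusion.** The point holds, in two parts. No stated analysis uses A1c although it is obtained for both groups, in a comparison that is open to confounding by prior control. The event and nadir bullets, if they cover non-participants as they appear to, compare groups with unequal night-time detection.

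The A1c bias is at most about 9 to 15 mg/dl for an imbalance of 0.3 to 0.5 points, and about 3 to 4 mg/dl at 30% carry-over. Neither the imbalance nor the carry-over is given in the documents. The detection ratio is 1.2 from the 3:45 AM check alone and higher with alert checks, by an amount that depends on assumed rates.

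A reader might infer that the trial's device effect is at risk. It is not: that effect comes from the randomised within-subject crossover, and the success criteria in VI. d. do not use non-participants. This is a low-cost improvement to a secondary comparison. It will not remove all confounding. For example, both trial arms follow a modified hypoglycemia rule that normal camp care does not.

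**What to change.** 1. **Adjustment.** In the non-participant regressions, add last pre-camp A1c to age and gender, and report how many non-participants lack a result. Add A1c, age and gender to the non-participant data list in VI. a., which omits all three. Report the date of each A1c, since non-participants have no recency limit while volunteers' values must fall within three months of screening. Cost: one covariate already being obtained. Non-participants without a result drop out of the adjusted model.
2. **Detection.** State whether the later event, nadir and range bullets cover non-participants. If so, compare events and nadirs on the shared pre-meal, bedtime and midnight readings, as the plan already does for mean BG and the percentage below 70 mg/dl. Keep the all-readings counts as descriptive, so that symptomatic lows are still reported. State that the range fractions use the same shared scheduled readings. Cost: a filter on readings, and fewer events in the matched comparison.

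Neither change affects study conduct or the co-primary analysis.

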### **Secondary endpoint analyses – CGM:**

- All of following metrics will be generated from the DexCom G4 Platinum CGM data during the closed-loop period and the usual care period, and the difference between the two periods will be reported unless otherwise specified. Each of these measures will be calculated for the entire period and separately for the full day and for the nighttime (11:00 PM to 7:00 AM).
- Mean CGMG
- Number of CGMG events < 70 mg/dl (episodes separated by < 15 minutes will be considered a single episode) and nadir for each
- Fraction of time spent within each of the following glucose ranges:

- < 70 mg/dl
- 70-120 mg/dl
- 70-180 mg/dl
- >180 mg/dl
- >250 mg/dl
- Area over the curve and below 70 mg/dl (measure of total hypoglycemia exposure)
- Area over the curve and below 50 mg/dl (measure of significant hypoglycemia exposure)
- Percentage of subjects with mean CGMG < 154 mg/dl
- Percentage of study days with mean CGMG < 154 mg/dl
- Mean CGMG in the four hour period following meals
- Mean CGMG during exercise (more active periods, periods of activity greater than walking intensity based on accelerometer data)
- Number of incidents of hypoglycemia and nadir CGMG during exercise
- Correlation between exercise intensity (based on accelerometer data) and likelihood of a hypoglycemic event by CGMG
- Risk of hypoglycemia and hyperglycemia >180 mg/dl and >250 mg/dl during hours with vs. without bionic pancreas downtime (closed-loop period only)
- Mean absolute relative deviation (MARD) of CGM vs. scheduled HemoCue BG measurements
- Standard deviation of CGM values
- Standard deviation of CGM values at night (11:00 PM to 7:00 AM)
- MARD vs. all HemoCue BG measurements Additional accuracy measures using all of the HemoCue measurements as the standard. Statistics will include:
- Median, quartiles, and mean absolute relative difference (MARD) and mean absolute difference (MAD) between CGM and BG reported separately in hypoglycemic (< 70 mg/dl), normoglycemic (70-120 mg/dl), postprandial target (70-180 mg/dl), hyperglycemic (> 180 mg/dl and > 250 mg/dl) ranges.
- Pearson and Spearman correlation coefficient between CGM and BG values reported separately in each range (hypoglycemic, normoglycemic, hyperglycemic).
- Intercept and slope of best-fit line for CGM to BG correlation plots
- Percent of CGM values meeting International Organization for Standardization (ISO) criteria (< 15 mg/dl difference for BG values < 70 mg/dl, < 20% absolute difference for BG values > 70) in each range.
- Clarke Error Grid Analysis (EGA) for all CGM and BG pairs in hypoglycemic, normoglycemic, post-prandial target, and hyperglycemic ranges. The data will be reported as fraction of values in zones A (clinically accurate), B (benign), zone C (overcorrect), zone D (failure to detect), and zone E (erroneous).
- Continuous Clarke Error Grid Analysis (EGA) for all CGM and BG pairs, including point- and rate-EGA (P-EGA and R-EGA) for each volunteer in hypoglycemic, normoglycemic, post-prandial target, and hyperglycemic ranges. The data will be reported as fraction of values in zones A (clinically accurate), B (benign), zone C (overcorrect), zone D (failure to detect), and zone E (erroneous).
- Reliability index calculated as percent of possible values actually recorded by CGM.
- MARD during periods with and without exercise (by 15 minute periods).
- Difference of outcome measures on day 1 vs. remaining days (days 2-5) and on day 1-2 vs. on remaining days (days 3-5)

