**Daily Routine:**

- Breakfast ~7:30 AM on weekdays, 8:00 AM on weekends\*\*
- Activity\*
- Activity\*
- Lunch 12:00PM\*\*
- Activity\*
- Activity\*
- Dinner 5:45 PM\*\*
- Activity\*
- Snack 8:30 PM\*\*
- 12:00 AM BG check (routine)

- 3:00 AM BG check if 12:00 AM check required intervention

\*Activity periods are divided by intensity into More Active and Less Active categories. Campers typically have two More Active and two Less Active periods daily.

\*\*BG checks are done 10–30 minutes before meals/snacks with insulin bolus 10–15 minutes before meals.

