- There is no area of the camp that is commonly visited by campers that is more than ~ 300 yards from any other area, so it will be easy for study staff to circulate and to get from one area to another if needed. Under the unusual circumstances when campers go further than this (i.e. for a hike) a study staff member will accompany that group carrying all needed supplies (which will also be duplicated by the camp RN/NG who will also accompany such groups. The remaining members of the study team will remain at the main camp area, maintaining the same ratio of study staff to subjects.
- Before disconnecting from the device for shower:
 

BG	Treatment
< 100 mg/dl	15g rapid acting carbohydrate
- Over the next five days (3:00 PM Sunday to 3:00 PM Friday) the bionic pancreas will control insulin and glucagon dosing and the volunteers will otherwise be treated according to camp guidelines except for specifically noted exceptions in the protocol.
- During closed-loop control the glucose measurements from the CGM will be transmitted to the bionic pancreas. The control algorithm will respond by commanding SC doses of insulin and/or glucagon as appropriate through the Tandem t:slim pumps.
- During the experiment the bionic pancreas device will be worn by the volunteer or kept nearby (such as when sleeping) at all times to ensure good radio-frequency signal reception. The device may be removed for short periods of time (no more than 30 minutes) for showering and swimming.
- If during the course of an experiment, a DexCom G4 sensor fails (reports sensor failure, ceases to transmit data, reports multiple calibration failures, or reports questionable data), the bionic

pancreas will automatically switch to giving basal insulin based on historical basal insulin needs at that time of the day. In addition, any BG measurements entered into the bionic pancreas will be used to dose insulin and glucagon as if they were CGM values and the system will continue to accept meal announcements. A new sensor will be inserted and closed-loop control will automatically resume once the new sensor is initially calibrated.

- Meals will be announced to the control algorithm 15-20 minutes prior to the meal at the same time as meal boluses are delivered for other campers. Low BG will be treated as usual, except that no action will be taken for  $BG > 70$  mg/dl.

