#### **During the closed-loop study period:**

- CGMG every five minutes from the DexCom G4 Platinum CGM
- HemoCue BG measurements before meals, snacks, bedtime, 12:00 AM and 3:45 AM
- Any additional HemoCue BG values
- Estimated carbohydrate intake (from camp healthcare provider documentation)
- Exercise and activity level (from camp schedule)
- Number of hypoglycemic events and nadir BG for each (from camp healthcare provider documentation)
- Number of carbohydrate interventions for hypoglycemia (from camp healthcare provider documentation)
- Insulin and glucagon doses administered by the control system
- Timing of meal announcements and size of meals announced
- Number of meal announcements
- Time between meal announcement and start of meal
- Meal and snack number, and timing
- Bionic pancreas downtime – number, timing, and duration of periods offline, reasons for being offline (CGM sensor loss, system crash, communication problem between CGM and bionic pancreas, communication problem between bionic pancreas and pumps, pump malfunction, tubing occlusion, infusion set failure/pulled out)
- Insulin bolus dosing in open-loop mode during CGM downtime
- Basal rate adjustments, including suspensions, during bionic pancreas downtime

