### **Secondary endpoint analyses – Non-glycemic:**

- All of following metrics will be generated from the closed-loop and usual care periods and the differences will be reported unless otherwise specified:
- Number of carbohydrate interventions for hypoglycemia (day and night)
- Total number of grams of carbohydrate taken for hypoglycemia (day and night)
- Insulin total daily dose
- Mean daily basal insulin dose
- Mean daily bolus insulin dose
- Number of carbohydrate interventions for hypoglycemia during the daytime (7:00 AM – 11:00 PM)
- Total number of grams of carbohydrate taken for hypoglycemia during the daytime ((7:00 AM – 11:00 PM)
- Number of carbohydrate interventions for hypoglycemia overnight (11:00 PM – 7:00 AM)
- Total number of grams of carbohydrate taken for hypoglycemia overnight (11:00 AM – 7:00 AM)
- Mean meal carbohydrate content
- The following metrics will be generated from the closed-loop period:
- Insulin lispro dosing (u/kg/24 hours)
- Glucagon dosing (mcg/kg/24 hours)
- Fraction of time bionic pancreas in open-loop mode due to loss of CGM signal
- Fraction of time bionic pancreas completely off-line
- Fraction of time bionic pancreas off-line or not functioning properly for each of the following reasons: system crash, communication problem between CGM and bionic pancreas, communication problem between bionic pancreas and pumps, pump malfunction, tubing occlusion, infusion set failure/pulled out
- Difference in mean insulin dose per hour during periods of normal operation vs. periods of bionic pancreas downtime
- Fraction of bionic pancreas downtime during which automatic basal rate suspended or reduced
- Difference in mean insulin dosing during the four hour period after a meal during periods of normal operation vs. periods of bionic pancreas downtime (open-loop dosing)
- Difference of outcome measures on day 1 vs. remaining days (days 2-5) and on day 1-2 vs. on remaining days (days 3-5)
- All of following metrics will be generated from the closed-loop, usual care periods, and from the non-participants and the differences will be reported unless otherwise specified:
- Number of carbohydrate interventions for hypoglycemia (day and night)
- Total number of grams of carbohydrate taken for hypoglycemia (day and night)
- Insulin total daily dose
- Mean daily basal insulin dose
- Mean daily bolus insulin dose
- Number of carbohydrate interventions for hypoglycemia during the daytime (7:00 AM – 11:00 PM)

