### **IX. Data and Safety Monitoring**

#### **IX. a. Monitoring of Source Data**

The principal investigator ([name]), a study clinical research fellow (physician), or a study nurse practitioner will review the eligibility of each volunteer based on the case report from the screening visit.

During the experiment, HemoCue and CGM data will be collected in various ways. CGM data, calibration data, insulin dosing data, and glucagon dosing data will be automatically stored in the bionic pancreas device (from which it will be downloaded at intervals) and wirelessly streamed to the monitoring station where it will also be stored electronically to provide redundancy in data storage and mitigate the risk of data loss. HemoCue BG data will be entered into the bionic pancreas immediately after determination and then wirelessly streamed with the rest of the data to the monitoring station. All of the data will be combined in a single database that will be compared against the primary data files for integrity. The computer database will be backed up at least monthly and the backup media stored in a secure location.

The Study will be conducted by the staff of the MGH Diabetes Research Center, the engineering research team at Boston University, and the staff of Camp Barton and Camp Joslin. The PI and engineering team will be involved in education of the staff prior to the start of the protocol and will communicate with study staff at least twice a week to review Study progress, discuss any issues in study conduct, and review procedures. Study staff will be encouraged to raise any concerns they may have or problems they have identified at any time. The PI, in consultation with the co-investigators, the staff of the camps, and the Medical Directors of the camp will decide a course of corrective action, and resolution or progress will be assessed no later than the next meeting.

An audit of procedures, regulatory documentation, and a sample of volunteer files is performed by a member of the Center at least biannually. The audit will be conducted by a Center staff member who is not directly involved in the conduct of the Study. This audit will include a review of regulatory documentation, such as IRB and FDA correspondence, and a review of volunteer files, including a

review of consents, case report forms, and other data from study visits.

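### The window for overnight hypoglycemia-carbohydrate grams is printed twice with an 11:00 AM start, against 11:00 PM elsewhere; two other groups of secondary endpoints have no listed data source

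*Combined protocol and SAP*

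**What the plan says.** **Overnight window.** The non-glycemic list in VI. b counts carbohydrate interventions for hypoglycemia, and sums their grams, by day and by night. Both daytime entries use 7:00 AM – 11:00 PM. The overnight count uses 11:00 PM – 7:00 AM, but the overnight grams entry is printed as 11:00 AM – 7:00 AM. The same pair of lines, with the same difference, returns in the block that adds the non-participants. The CGM list in VI. b sets night at 11:00 PM to 7:00 AM.

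**Exercise.** Two CGM endpoints name an accelerometer: "Correlation between exercise intensity (based on accelerometer data) and likelihood of a hypoglycemic event by CGMG" and "Mean CGMG during exercise (more active periods, periods of activity greater than walking intensity based on accelerometer data". Both study-period lists in VI. a instead give "Exercise and activity level (from camp schedule" as the activity item. Section IX. a states that "CGM data, calibration data, insulin dosing data, and glucagon dosing data will be automatically stored in the bionic pancreas device", with no mention of motion data.

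**Non-participant insulin.** The last non-glycemic block opens with "All of following metrics will be generated from the closed-loop, usual care periods, and from the non-participants" and includes total daily, basal and bolus insulin. The non-participant list in VI. a has no insulin item, and the permission described in IV. a covers glucose values, hypoglycemia interventions and the last A1c.

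**The concern.** The clock window is a stated rule for calculating an endpoint. A programmer who followed it would sum overnight grams over different hours from the overnight count printed beside it. The two could then not be read together, and a closed-loop effect on nocturnal treatment would be mixed with daytime treatment.

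The other two items are gaps between what is to be analysed and what is listed as collected. A correlation with exercise intensity needs a graded measure, and the listed source offers only two classes: "Activity periods are divided by intensity into More Active and Less Active categories". For insulin, volunteers' usual-care doses come from a pump download. If non-participants' figures came from written orders, the comparison would set ordered doses against delivered doses, which are different quantities.

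**Working it through.** **1. Overnight window**

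All inputs are the windows printed in VI. b. First, the plan's own day and night:

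- Daytime, 7:00 AM – 11:00 PM: 23 − 7 = 16 h.
- Night, 11:00 PM – 7:00 AM (overnight count, and CGM night): 1 + 7 = 8 h.
- Sum: 16 + 8 = 24 h, with no overlap. These two windows divide the day exactly.

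Now the window printed for overnight grams:

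- 11:00 AM – 7:00 AM: 13 h to midnight + 7 h = 20 h.
- Overlap with daytime, 11:00 AM – 11:00 PM: 12 h, and 12/16 = 75% of daytime hours.
- Sum of daytime and printed overnight: 16 + 20 = 36 h of a 24 h day.
- Over a five-day period: 5 × 20 = 100 h, against 5 × 8 = 40 h.

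In grams, let D be the daytime total, N the total for 11 PM – 7 AM, and M the part of D taken from 11 AM to 11 PM (0 ≤ M ≤ D). The printed overnight endpoint equals N + M instead of N. Daytime plus printed overnight equals D + N + M. The plan's separate day-and-night total is D + N, so the parts exceed the whole by M. The plan does not say how treatments spread over the day, so M could be any part of D. It would be 75% of D only if daytime grams fell evenly over the 16 hours.

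**2. Accelerometer**

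| Place | Activity or motion source |
|---|---|
| VI. b, CGM endpoints | Accelerometer: one endpoint wholly, one in part |
| VI. a, usual care list | Camp schedule; 0 of 8 items name an accelerometer |
| VI. a, closed-loop list | Camp schedule; 0 of 15 items name an accelerometer |
| V. c, Devices | Infusion sets, CGM, control unit with a stock phone, pumps, glucose meter; no motion logging described |
| IX. a, data stored in the device | CGM, calibration, insulin and glucagon data |
| V. d. iii, usual care procedures | Camp staff log, camper by camper, which sessions were active and which less active |

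Mean CGM glucose during exercise can be computed from the schedule, because its definition also admits the camp's more active periods. The correlation cannot be computed as defined without a motion source.

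**3. Non-participant insulin**

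Three metrics (total, basal, bolus) are to be compared. In the non-participant list of VI. a, 0 of 6 items are insulin, and IV. a does not name it. Section V limits non-participants to chart review. The only pump download described, in the usual care procedures of V. d. iii and the matching data list, is for study volunteers.

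**The case against.** The strongest reply is that these are drafting slips, and much of it stands.

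- **Window.** The endpoint is labelled overnight, the line before it says 11:00 PM, and the daytime window ends at 11:00 PM. The intended window is clear, and the second entry repeats the slip in a repeated block. That supports calling it a typing error. It does not remove the need to correct a printed rule.
- **Lists.** The data lists are not exhaustive. Non-participant A1c is sought in IV. a but absent from their list in VI. a. Grams given for hypoglycemia are in neither volunteer list, yet V. e has the amount and time of each treatment recorded. Absence from a list therefore shows an unnamed source, not uncollected data.
- **Other places the data may sit.** The stock phone might log motion; the text neither states nor excludes it. Camp charts may hold insulin orders or doses, since the camp physician writes the orders and camp staff supervise administration (V. d. ii). The camp medical manual, cited as Appendix D, is not in the text available here and may settle this.

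A reader might infer that most daytime carbohydrate would be counted twice. The documents do not support that: the 75% is a share of hours, and the endpoint covers only carbohydrate given for hypoglycemia, not meals. A reader might also infer that the accelerometer or insulin data cannot be obtained, that sources would be picked once results are known, or that the non-participant information sheet must be rewritten. None of these is shown; the sheet's contents are not given in the available text.

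**Conclusion.** The overnight grams window is wrong as printed in two entries: 20 h against the 8 h night used elsewhere, overlapping 12 of 16 daytime hours. It is very likely a typing error. The effect in grams is unknown, and arises only if the printed window is followed literally.

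The other two are consistency notes of lesser weight. Two CGM endpoints cite accelerometer data, and three insulin comparisons include non-participants, with no source listed in the available text. The conclusion there is that the source is not named, no more.

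Every affected endpoint is secondary. The co-primary endpoints in VI. b rest on scheduled HemoCue values, and the success criteria in VI. d on mean glucose, time below 70 mg/dl, severe hypoglycemia and comparative glycemic control. None of these uses carbohydrate grams, motion data or insulin dose. Severity is minor.

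**What to change.** 1. **Window.** Change both overnight grams entries to 11:00 PM – 7:00 AM. This costs two one-letter edits.

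2. **Exercise.** Before the camp sessions, choose one of two routes.
   - Name the motion source in V. c and in both study-period lists of VI. a, and collect it the same way in both arms. If the source is the control unit, say how time off the device is handled, since "The device may be removed for short periods of time (no more than 30 minutes) for showering and swimming".
   - Or drop the correlation and define exercise in both arms from the camper-by-camper activity log already planned in V. d. iii. State that the log is kept in the closed-loop period too and that it records start and end times. The daily routine in V. d. ii prints no times for activity periods, while the CGM list also asks for "MARD during periods with and without exercise (by 15 minute periods". The cost is some extra recording and a two-class measure in place of a graded one.

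3. **Non-participant insulin.** Either delete the three comparisons, or add delivered insulin dose and its chart source to IV. a and to the non-participant list in VI. a. If insulin is kept, settle this before the first non-participant is asked for consent, and check that the information sheet covers it. Deletion is the cheaper route.
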